m. CT or MRI with contrast, of the neck, chest, abdomen, and pelvis are acceptable (PET/CT is not allowed for study assessments, unless CT is done with IV contrast). Images will be repeated every 8 weeks (± 3 days) during treatment period until disease progression. During the Long-term Follow-up visit, only in patients who discontinued investigational product due to toxicity, radiographic imaging will be done every 3 months until disease progression or until patient initiates another anti-cancer therapy. The same radiographic technique of each region must be used consistently throughout the study. Refer to Imaging Manual. A repeat of tumor imaging will be required for the purposes of confirmation of response (i.e., partial response, and/or complete response). The confirmation scan should be no earlier than 4 weeks following the first indication of response. n. Quality of life questionnaire will be administered every 4 weeks before investigational product administration or receipt of radiological imaging results

o. For blood mRNA pharmacodynamic biomarker assessments, blood will be drawn on C1D1 and C1D22 at pre-dose (within 1 hour before start of dose), 7 hours (± 1 hour, and 24-48 hours after start of infusion (± 1 hour), C1D8 pre-dose (within 1 hour before start of dose), C2D1 pre-dose (within 1 hour before start of dose), every odd cycle Day 22 predose (within 1 hour before start of dose), and at confirmed progression. In addition, a blood sample will be collected on the day of the on-treatment biopsy (Cycle 4, Day 1 ± 28 days).

p. For blood cfDNA biomarker assessments, blood will be drawn on C1D1 and C2D1 at pre-dose (within 1 hour before start of dose), and every odd cycle Day 22 pre-dose (within 1 hour before start of dose), and at confirmed progression. In addition, a blood sample will be collected on the day of the on treatment biopsy (Cycle 4, Day 1 ± 28 days). q. During Cycle 1, population PK blood samples will be collected as follows:

Dose No. in a given cycle	Cycle / Day	Nominal Day	Hours Relative to Dose (Window)
1	Cycle 1 / Day1	1	Pre-dose (within 1 hour before start of dose) End-infusion (within 10 minutes of infusion end) 2 hours after start of infusion (± 30 minutes) 4 hours after start of infusion (± 1 hour) 7 hours after start of infusion (± 1 hour)
1	Cycle 1 / Day 2 or 3	2 or 3	24 - 48 hours after start of infusion (± 1 hour)
2	Cycle 1 / Day 8	8	Pre-dose (within 1 hour before start of dose)

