6.4.1.2 Secondary Efficacy Variables

Secondary efficacy endpoints include the following:

Duration of Response (DOR): defined as the time interval from the initial confirmed response of CR or PR to the earlier of the first documentation of disease progression (per RECIST v1.1 or modified MDA criteria) or death from any cause, as determined by Investigator review. DOR will be calculated in months as (date of disease progression or death/censoring – date of initial response + 1) / 30.4375.

For DOR (and PFS) the date of progression or death and censoring will be based on the Food and Drug Administration (FDA) guidance *Clinical Trial Endpoints for the Approval of Cancer Drugs and Biologics* (May 2007), as defined in Table 7.

Table 7 Determining Date of Progression or Censoring for PFS and DOR Analysis

Situation	Date of Progression or Censoring	Outcome
Alive and without documentation of disease progression.	Date of last disease assessment. All patients still alive and without documentation of disease will be censored as of July 31, 2022.	Censored
Treatment discontinuation for undocumented progression	Date of last disease assessment	Censored
Treatment discontinuation for toxicity or other reason	Date of last disease assessment	Censored
Other anticancer treatment started before documentation of disease progression or death	Date of last disease assessment prior to start of other anticancer treatment	Censored

Death before first disease assessment	Date of death	Progressed
Death or disease progression between planned disease assessments	Date of death or first disease assessment showing disease progression, whichever occurs first	Progressed
Death or progression after more than one missed disease assessment	Date of last disease assessment visit without documentation of disease progression that is before the first missed visit	Censored

As part of the sensitivity analysis, DOR will also be derived as follows:

- As above but where confirmation of PR/CR is not required.
- As above but based on central review rather than Investigator review.
- As above but based on central review rather than Investigator review and where confirmation of PR/CR is not required.

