Progression-Free Survival (PFS): defined as the interval from the start of investigational product to the earlier of the first documentation of disease progression (per RECIST v1.1 or modified MDA criteria) or death from any cause, as determined by Investigator review. Progression-free survival will be defined in months as: (date of progression or death/censoring – date of first infusion + 1) / 30.4375.

Patients without disease progression or death will be censored as per Table 7.

As part of the sensitivity analysis, PFS will also be derived as follows:

- As above but based on central review rather than Investigator review.

Overall Survival (OS): defined as the time from the date of start of treatment to the date of death from any cause. Subjects with no documentation of death will be censored at the last date known to be alive, per the data collection. Sites will be asked to search public registries for any possible death dates for subjects who withdrew consent from the study (as per FDA Guidance for Sponsors, Clinical Investigators, and IRBs

Data Retention When Subjects Withdraw from FDA-Regulated Clinical Trials). Where it is possible for this search to be done, any deaths found will be included in the analysis. Overall survival time will be calculated in months as (date of death/censoring – date of first infusion + 1) / 30.4375.

As part of the sensitivity analysis, OS will also be derived as follows:

- As above but where date of first diagnosis of recurrent or metastatic disease is used instead of date of first infusion.
- As above but where date of initial ACC diagnosis is used instead of date of first infusion.

Time to Response (TTR): defined as the interval from the start of investigational product to the initial (subsequently confirmed) response of CR or PR (per RECIST v1.1 or modified MDA criteria), as determined by Investigator review. TTR will be calculated in months as $(\text{date of initial response/censoring} - \text{date of first infusion} + 1) / 30.4375$.

Patients without response will be right censored at their last tumor assessment.

As part of the sensitivity analysis, TTR will also be derived as follows:

- As above but where confirmation of PR/CR is not required.
- As above but based on central review rather than Investigator review.
- As above but based on central review rather than Investigator review and where confirmation of PR/CR is not required.

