7.5.3 Secondary Endpoint Analysis Methods

All secondary efficacy endpoints will be analyzed in each cohort independently. There will be no adjustment for multiplicity among the secondary endpoints. The primary analysis of each secondary endpoint will be conducted using the Efficacy Evaluable analysis set. Sensitivity analyses will be conducted using alternative analysis sets as described in each section below.

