7.5.3.1 Duration of Response

The Kaplan-Meier method will be used to analyze DOR. The Kaplan-Meier curves will be plotted. Counts and percentages for number of subjects who experienced the event of interest and those who are censored will be presented along with minimum and maximum duration in months. The median, 25th and 75th percentiles will be estimated and their corresponding Brookmeyer-Crowley 95% CIs using the Kaplan-Meier estimates. Landmark estimates will be provided for 2, 4, 6 and 8 months after start of investigational product.

The following sensitivity analyses will be conducted:

- The DOR analysis will be repeated using the PP analysis set;
- The DOR analysis will be repeated using unconfirmed response;
- The DOR analysis will be repeated using central read based on confirmed response;

□

The DOR analysis will be repeated using central read based on unconfirmed response.

Subgroup analyses will not be performed for DOR due to the small number of responders.

DOR will be displayed graphically by patient and cohort using swimmer plots.

7.5.3.2 *Progression Free Survival*

PFS will be summarized similarly to DOR using the Kaplan-Meier method and estimates will be presented along with Brookmeyer-Crowley 95% CIs. Appropriate landmark estimates will also be included.

The following sensitivity analyses will be conducted:

- The PFS analysis will be repeated using the PP analysis set;
- The PFS analysis will be repeated using central read;
- The PFS analysis will be repeated using the subset of subjects with a BOR of PR (BOR will be based on the Investigator results irrespective of confirmation; PFS will be based on the Investigator results).

Subgroup analyses will also be performed based on the main subgroups outlined above for ORR. Kaplan-Meier curves will be plotted for each subgroup.

7.5.3.3 *Overall Survival*

OS will be summarized similarly to DOR using the Kaplan-Meier method and estimates will be presented along with Brookmeyer-Crowley 95% CIs. Appropriate landmark estimates will also be included.

The following sensitivity analyses will be conducted:

- The OS analysis will be repeated using the PP analysis set;
- The OS analysis will be repeated using the Safety analysis set;
- The OS analysis will be repeated using the subset of subjects with a BOR of PR (BOR will be based on the Investigator results irrespective of confirmation).

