Additional analyses of OS will be conducted using the same methods as outlined above, with the following changes to the definition of OS:

□

Calculated using date of first recurrent or metastatic disease instead of date of first infusion as time 0 (the same rules as detailed in Section 7.4.3 will be used to impute partial dates and in some cases, missing, dates);

- Calculated using date of initial ACC diagnosis instead of date of first infusion as time 0 (the same rules as detailed in Section 7.4.3 will be used to impute partial dates).

Subgroup analyses will also be performed based on the main subgroups outlined above for ORR. Kaplan-Meier curves will be plotted for each subgroup.

7.5.3.4 *Time to Response*

TTR will be summarized similarly to DOR using the Kaplan-Meier method and estimates will be presented along with Brookmeyer-Crowley 95% CIs. Appropriate landmark estimates will also be included.

The following sensitivity analyses will be conducted:

- The TTR analysis will be repeated using the PP analysis set;
- The TTR analysis will be repeated using unconfirmed response;
- The TTR analysis will be repeated using central read based on confirmed response;
- The TTR analysis will be repeated using central read based on unconfirmed response.

Subgroup analyses will also be performed based on the main subgroups outlined above for ORR. Kaplan-Meier curves will be plotted for each subgroup.

7.5.3.5 *Disease Control Rate*

DCR will be summarized similarly to ORR.

The following sensitivity analyses will be conducted:

- The DCR analysis will be repeated using the PP analysis set;
- The DCR analysis will be repeated using unconfirmed response;
- The DCR analysis will be repeated using central read based on confirmed response;

□

The DCR analysis will be repeated using central read based on unconfirmed response.

Subgroup analyses will also be performed based on the main subgroups outlined above for ORR. The results will be displayed graphically in forest plots.

7.5.3.6 *Change in EORTC QLQ-C30*

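### Kaplan-Meier time to response censors non-responders at their last scan, so estimates beyond the first scan can overstate the probability of response

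*SAP*

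**What the plan says.** SAP 6.4.1.2 defines TTR as "the interval from the start of investigational product to the initial (subsequently confirmed) response of CR or PR". For everyone else it says: "Patients without response will be right censored at their last tumor assessment".

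SAP 7.5.3.4 gives the estimator: "TTR will be summarized similarly to DOR using the Kaplan-Meier method and estimates will be presented along with Brookmeyer-Crowley 95% CIs". It adds landmark estimates, without naming the time points, and Kaplan-Meier curves by subgroup. The DOR section that it points to (7.5.3.1) states: "The median, 25th and 75th percentiles will be estimated".

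The population is set in SAP 7.5.3: "The primary analysis of each secondary endpoint will be conducted using the Efficacy Evaluable analysis set". Responders and non-responders are thus analysed together.

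The only detailed censoring table, SAP Table 7, is titled "Determining Date of Progression or Censoring for PFS and DOR Analysis" and does not cover TTR. The four TTR sensitivity analyses in 7.5.3.4 change the analysis set, the confirmation requirement or the reader. None changes the censoring rule.

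**The concern.** Kaplan-Meier is valid here only if a patient censored at a given time would have gone on to respond at the same rate as those still at risk. Most non-responders leave the risk set for a reason that makes this implausible. Under footnote m of SAP Table 2, imaging is repeated "during treatment period until disease progression", and later imaging is kept only for patients who stopped for toxicity. A progressor's last tumor assessment is therefore normally the progression scan or the end-of-study scan. Death and new anticancer therapy end the scans in the same way.

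Removing these patients shrinks the denominator for every later response. 1-KM then sits at or above the proportion who have actually responded. The excess depends on how early patients progress, so two subgroups with identical responses could show different TTR curves. The report would also place an ORR beside a TTR curve that appears to promise a higher response probability in the same patients.

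**Working it through.** The plan states no figure for TTR, so there is none to reproduce. The check compares two estimators on the same data:

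- **SAP rule:** 1-KM(t) = 1 - product over response times up to t of (1 - d/n), where d is the number responding and n the number still at risk. Responses are ranked before censorings at tied times.
- **Cumulative incidence, with progression as a competing event:** if there is no other loss before the last response, this equals responders by time t divided by N.

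**Example 1: assumed cohort of 42 with 7 responders.** N = 42 is the Cohort 2 maximum. The timing is assumed: 4 responses at week 8, 2 at week 16 and 1 at week 24. In the heavier case 16 non-responders progress at week 8 (38%, close to the interim 39%) and 8 at week 16. In the lighter case 8 progress at each of those weeks. All others are followed to week 24 or beyond.

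Numbers at risk:
- Heavier: 42; then 42 - 4 - 16 = 22; then 22 - 2 - 8 = 12.
- Lighter: 42; then 42 - 4 - 8 = 30; then 30 - 2 - 8 = 20.

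Weeks are converted by the SAP formula, for example (56 + 1)/30.4375 = 1.9 months.

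| Scan | Responded / 42 | 1-KM, heavier | 1-KM, lighter |
|---|---|---|---|
| Week 8 (1.9 mo) | 4/42 = 9.5% | 1 - 38/42 = 9.5% | 9.5% |
| Week 16 (3.7 mo) | 6/42 = 14.3% | 1 - (38/42)(20/22) = 17.7% | 1 - (38/42)(28/30) = 15.6% |
| Week 24 (5.6 mo) | 7/42 = 16.7% | 1 - (38/42)(20/22)(11/12) = 24.6% | 1 - (38/42)(28/30)(19/20) = 19.8% |

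A 2-month landmark is unbiased, and the excess appears from week 16. The two cases have the same 7 responses at the same weeks, so the 4.8-point gap between 24.6% and 19.8% comes from progression alone.

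**Example 2: the interim mix.** Protocol 1.3.2 reports 4 PR, 7 SD and 7 PD among 18 evaluable patients. Assumed timing: PD censored at week 8, SD at week 24, k responses at week 8 and 4 - k at week 16. The number at risk at week 16 is 18 - k - 7 = 11 - k, so final 1-KM = 1 - ((18 - k)/18) × (7/(11 - k)).

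| k at week 8 | Final 1-KM | Responded |
|---|---|---|
| 4 | 1 - (14/18)(7/7) = 22.2% | 4/18 = 22.2% |
| 3 | 1 - (15/18)(7/8) = 27.1% | 22.2% |
| 2 | 1 - (16/18)(7/9) = 30.9% | 22.2% |
| 1 | 1 - (17/18)(7/10) = 33.9% | 22.2% |
| 0 | 1 - 7/11 = 36.4% | 22.2% |

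The excess runs from 0 to 14.2 points. In four of the five timings 1-KM passes 25% at week 16. A 25th-percentile TTR would then be reported although fewer than a quarter of patients ever responded.

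**End-of-study scan.** Protocol Table 2 requires imaging 30 days after the last dose. A patient who stops at a week-8 progression would then be censored near week 12, and at week 16 near week 20. Both still fall before the next scheduled scan, so neither table changes.

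**The case against.** The strongest reply is that little rests on TTR. The primary endpoint is ORR with exact limits (SAP 7.5.2), and patients without evaluable response data count as non-responders (7.5.4.2). SAP 7.5.4.4 describes the study as exploratory, and 7.10 discloses TTR as an added secondary endpoint. The true ORR, with the same subgroups, will stand in the same report. All of this is correct and limits the consequence, but it does not make the estimator right.

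Four stronger readings are tempting, and the documents do not support them:

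- **A reader might infer that every TTR estimate carries the same upward bias.** It does not. The bias is zero at the first-scan landmark in Example 1, and throughout Example 2 if all responses occur at week 8. The SAP does not name the TTR landmarks, so which would be affected is unknown.
- **A reader might infer that progression ends all chance of response.** SAP 6.1 allows treatment beyond radiological progression with approval, and the BOR window in 6.4.1.1 closes at subsequent anticancer therapy. A few late responses are possible, but they do not make the censoring non-informative.
- **A reader might infer that the TTR curve contradicts the ORR.** The two are different quantities. The fault is that 1-KM will be read as a response probability.
- **A reader might infer that all treated patients are involved.** The Efficacy Evaluable set requires a post-baseline tumor assessment, so deaths before any scan do not enter.

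It could also be argued that a footnote to the Kaplan-Meier output would do. That would warn the reader but leave biased landmarks and quantiles in the tables.

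**Conclusion.** The concern holds in a limited form. The censoring rule for TTR is informative, no passage treats progression, death or new therapy as a competing event, and no planned sensitivity analysis removes the problem. After the first scan, 1-KM landmarks and quantiles can overstate the cumulative probability of response and exceed the ORR in the same patients.

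The bias grows with later responses and earlier progression. The documents give no response timing, so the size cannot be fixed: about 3 to 8 points in the assumed cohort of 42, and 0 to 14 points with the interim mix. These figures rest on the assumed scan weeks, follow-up of all other patients past the last response, and response ranked before censoring at ties. The primary ORR is not affected and no hypothesis test depends on TTR. This should be corrected, but it does not threaten the trial's main conclusion.

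**What to change.** In SAP 6.4.1.2 and 7.5.3.4:

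1. Summarise TTR descriptively in responders only: median, Q1, Q3 and range. Remove the rule that right censors non-responders.
2. If a curve, landmarks or subgroup curves over all evaluable patients are wanted, replace 1-KM with the cumulative incidence function, with progression, death and new anticancer therapy as competing events. Apply the same change to the sensitivity versions.
3. State whether a response after progression counts for patients treated beyond progression, consistent with the BOR window in 6.4.1.1.

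The data are already collected. The cost is minor SAP and programming work with a standard procedure, and a slightly less favourable curve.

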6.4.2.2 Medical History and Concomitant Medications

Any clinically significant diseases including any co-morbid conditions requiring active treatment as well as significant surgeries will be documented in the medical history section of the eCRF. This includes prior medical history and treatment regimens for ACC. Verbatim terms on case report forms will be mapped to preferred terms and system organ classes using the Medical Dictionary for Regulatory Activities (MedDRA, version 23.0) and will be summarized by SOC and PT.

Abnormal physical examination finding and/or the diagnosis of concomitant disease resulting from assessments at Screening will also be documented in the medical history section. Information on all interventions (systemic therapy, surgery, radiation treatment) related to the subject's cancer will also be collected. Radiology and photography reports from imaging conducted as routine care will be collected if available from the last 3 years.

Concomitant medication is defined as any prescription or over-the-counter preparation, including vitamins and supplements. Use of concomitant medication from 28 days before Day 1 of Cycle 1 through 30 days after the last dose of investigational product will be recorded. Concomitant medications will be coded according to the WHO Drug dictionary and will be summarized according to the coded terms.

6.4.2.3 Eastern Cooperative Oncology Group Performance Status

The Eastern Cooperative Oncology Group (ECOG) Performance Status will be collected at all study visits and be used to assess the subjects' performance status.

6.4.2.4 Vital Signs

Vital signs will be measured at all study visits and will include heart rate, respiratory rate, temperature, and blood pressure (systolic and diastolic). Blood pressure and heart rate will be done at rest as per standard practice at the investigational site.

6.4.2.5 *12-Lead Electrocardiogram (ECG)*

Single 12-Lead ECG will be performed at the Screening, every 12 weeks, and the End of Study visits. Twelve-Lead ECG will be obtained using an ECG machine that automatically calculates the heart rate and measures PR, QRS, QT, and QTc intervals. Triplicate ECGs, at least 3 minutes apart, will be performed if QTcF is > 500 msec or if the Investigator identifies an ECG finding that is an adverse event and related to the investigational product. Subjects should be in the supine position and the ECG should be performed after the subject has rested for at least 5 minutes.

6.4.2.6 *Physical Examination*

The complete physical examination will include appearance, eyes, ears, nose, head, throat, neck, lungs, heart, abdomen, extremities, skin, and musculoskeletal system and will be performed at the Screening, Cycle 1 Day 1, and End of Study visits. Symptom directed physical examinations will be conducted on all subsequent study visits.

Height will be recorded at Screening only and weight measurements using a medical scale will be recorded at each study visit.

6.4.2.7 *Laboratory Parameters*

Safety laboratory assessments will be performed by local laboratories. Screening laboratory results may be used for Cycle 1 Day 1 (C1D1) if conducted within 3-7 days.

The laboratory evaluations will include, but are not limited to:

- Hematology/CBC including hemoglobin, hematocrit, platelet count, white blood cell (WBC) count, and absolute differential count.
- Peripheral blood lymphocytes subsets; this may include percent of B cells, T cells, NK cell, T-Helper cells, T cytotoxic (killer) cells, T reg (suppressor) cells and macrophages.
- Serum chemistry: sodium, potassium, chloride, blood urea nitrogen (BUN), creatinine, total bilirubin, albumin, aspartate aminotransferase (AST), alanine aminotransferase (ALT), alkaline phosphatase, lactate dehydrogenase (LDH), sodium, potassium, chloride, bicarbonate, glucose, calcium, magnesium, phosphorus. A direct bilirubin should be obtained if the total bilirubin level is > 1.5 times ULN. Creatinine clearance will be done at Screening only. Lipase will also be measured in patients experiencing diarrhea.

- Coagulation assessment, including: prothrombin time (PT), and activated partial thromboplastin time (aPTT).
- Serology: HBsAg, HCV RNA (qualitative) and HIV.
- Urinalysis (dipstick): pH, glucose, ketones, protein, specific gravity, bilirubin and evidence of infection; microscopic examination will be done when findings are abnormal.
- Urinalysis (dipstick): pH, glucose, ketones, protein, specific gravity, bilirubin and evidence of infection; microscopic examination will be done when findings are abnormal.
- Other safety labs: HbA1c, thyroid panel, triglycerides, and prostate specific antigen.

6.4.2.8 *Other Safety Variables*

Women of childbearing potential will have a urine or serum pregnancy test every cycle.

6.4.3 *Description of Pharmacokinetic Variables*

Blood samples for population pharmacokinetics will be collected as detailed in the schedule of activities. The date, time, and scheduled time point of the collection, along with a reason if the sample is not collected, will be recorded on the eCRF.

